The inconsistency of correct determination of body position of this accelerometer model when worn around the waist has been demonstrated by other authors (Berendsen et al., 2014, Hänggi et al., 2013). The inconsistency of correct identification of the sitting position in particular was highlighted by (Hänggi et al., 2013). Other researchers have investigated ways of improving the ability to correctly classify the sitting position (Skotte et al., 2014). The study by (Skotte et al., 2014)

determined that the addition of a second Actigraph GT3X accelerometer placed on the mid-thigh yielded excellent results in detection of the sitting position. Pressure sensors in subjects' hip pockets were used as a criterion measure to classify body position.

As mentioned previously, the feasibility undertaken by the CI determined that the ankle placement was superior to the waist for recognition of step count. When walking a ten metre distance with a walking aid, using observed step count as a criterion measure the ankle placement demonstrated a mean difference -1 step, (Limits of Agreement (LOA) +3 to -5 steps) compared to the waist placement (mean difference -7 steps, LOA +9 to -23 steps). These positive findings for step count for the ankle placement are supported by a recent study cited earlier using a similar Actigraph model investigating the accuracy of step count in older adults (Korpan et al., 2015).

Defining the research question

Using the findings from the feasibility study regarding the ankle placement of the Actigraph GT3X accelerometer and the research cited suggesting improved classification of the sitting position with the addition of a thigh mounted accelerometer the following research question is proposed:

Can an Actigraph GT3X accelerometer, placed at the ankle and thigh of the same leg, accurately measure body position and walking episodes undertaken by patients recovering from critical illness in a hospital ward?

A number of study objectives evolve from this research question, assisting in the development of the methodological processes required to answer it.

1. To determine the criterion validity of the ActiGraph GT3X accelerometer in detection of body position and step count when positioned either on the mid-thigh or ankle of the same leg.
2. To establish if there is a superior single body placement site (thigh or ankle) to objectively record body position and step count within this patient population.

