Participants will be free to undertake the activities within the semi-structured movement protocol in any order they prefer. Whilst undertaking the movements, participants will be observed by the CI. Although there is a requirement for the CI to be able to visualise them, the actual distance that she is from the patient will be determined according to the individual's wishes. Respect for privacy and dignity will be of paramount importance. Participants will not be observed if they are using a commode, the toilet or if bathing. The accelerometer data downloaded during these periods of time will be excluded from data analysis. A digital clock with an hour, minute and second display, successfully employed within the feasibility study will be used to note the time (to the hour, minute and second) when a particular movement or postural change occurred and ended. Once a postural change ends, a further five seconds will be observed on the digital clock before the new body position is documented as complete. This is to accommodate findings from the feasibility study and subsequent manufacturers recommendations related to how the accelerometer models process information. The digital clock will be synchronised to the time setting on a laptop computer, which will also be used to activate the desired settings on both accelerometers (termed 'initialisation'). These

processes will occur immediately before the data collection period to maximise synchronisation of the digital clock with the time setting on the accelerometers. The laptop computer will not be used during data collection, only for time synchronising the digital clock and for initialising the settings onto both accelerometers. The accelerometers will be programmed to capture data every second (one second epoch).

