A sample size of 20 participants will be recruited. This sample size has been used in previous research investigating the validity of a different accelerometer model to quantify gait parameters in patients recovering from critical illness (Edbrooke et al., 2012). They predicted that 12 subjects were necessary based upon alpha = 0.05 (significance level), beta = 0.9 (power) and a correlation of $r = 0.75$, categorised as a good to excellent correlation (Trapp and Dawson, 2004). A sample size of 20 was also recruited in another study investigating the validity of accelerometer measurement within a hospitalised stroke population (Kramer et al., 2013). Recruiting a sample of 20 patients will permit some attrition should there be any accelerometer malfunction or decisions to withdraw, yet supply an achievable number for participant recruitment based on feedback from clinical colleagues working within the specialty.

Statistical analysis

IBM SPSS statistics (Version 20) will be used to undertake statistical analysis. Some data captured by the accelerometers is continuous and others categorical.

Categorical data

Categorical data, concerning body position (lying, sitting or standing) will be analysed using the Kappa statistic, calculating agreement between the accelerometer inclinometer data and direct observation. Each accelerometer placement site (thigh and ankle) will initially be analysed separately. Examination of the inclinometer raw data captured from both placement sites will determine whether an algorithm can be constructed using readings from both the ankle and thigh placement to improve determination of the sitting

position specifically if necessary. Direct observation will serve as the criterion measure for all the analyses.

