Percentage agreement of inclinometer raw data from the thigh and ankle accelerometers with direct observation for detection of each separate body position will be calculated. A further percentage agreement analysis will be undertaken if an algorithm can be constructed for determination of the sitting position using readings from both placement sites. This algorithm will be compared against direct observational raw data identifying the sitting position only. This result will be compared against the percentage agreement of the individual placement sites in determination of the sitting position. This will assist in determination of whether the algorithm is more superior to a single placement site in determination of the sitting position.

Continuous data

Agreement between step count recorded by each accelerometer placement site and direct observation (manual counts) as a criterion measure will be determined using Bland Altman analysis with 95% limits of agreement (LOA).

Acceptance of the devices over a three-hour period

The statements within the Likert scale will be collapsed to obtain true positives (very comfortable and somewhat comfortable) and true negatives (very uncomfortable and somewhat uncomfortable). The middle category (neither comfortable nor uncomfortable) will remain a separate category. A descriptive analysis will be undertaken to investigate this particular aspect of enquiry using percentages of true positives, the middle category and true negatives. This will be presented graphically.

Any specific comments made by the patients in relation to acceptability of the devices will be included as free text within the results section. The statements will be anonymous and permission from participants will be sought regarding their inclusion within the body of the thesis or publications which may arise from it.

Ethics approval

This study has received approval from the NHS Local Research Ethics Committee (REF: XXXXX) and the Research Ethics Sub Committee, YSJU (REF: XXXXXX).

Data handling and confidentiality

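### Objective 2 asks whether thigh or ankle is the better single site, but the plan analyses each site separately, with no paired contrast and no interval for kappa or percentage agreement

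*Combined protocol and SAP*

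**What the plan says.** Objective 2, under Defining the research question, reads "To establish if there is a superior single body placement site (thigh or ankle) to objectively record body position and step count". It is a comparative question about two outcomes.

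The analysis of position is under Statistical analysis, Categorical data. Body position "will be analysed using the Kappa statistic, calculating agreement between the accelerometer inclinometer data and direct observation", and "Each accelerometer placement site (thigh and ankle) will initially be analysed separately". The same section adds "Percentage agreement of inclinometer raw data from the thigh and ankle accelerometers with direct observation for detection of each separate body position". If an algorithm combining the two sites can be built, its agreement for sitting is set against that of each single site: "This will assist in determination of whether the algorithm is more superior to a single placement site in determination of the sitting position".

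For steps, Continuous data plans Bland-Altman analysis with 95% limits for "Agreement between step count recorded by each accelerometer placement site and direct observation (manual counts) as a criterion measure".

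The row of the kappa table is not defined. Study procedure sets a one-second recording epoch, and the observer is to "note the time (to the hour, minute and second) when a particular movement or postural change occurred and ended". The analysis section refers to raw inclinometer data. The denominator for per-position agreement is not given either.

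**The concern.** The plan gives results for each site but no analysis of the difference between them. The algorithm comparison does not fill the gap: it covers sitting only and asks whether two devices beat one. Limits of agreement describe how far one site's counts scatter around the manual count. They are not an interval for a site difference.

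Objective 2 would therefore be answered by placing two kappas, two sets of percentages and two pairs of limits side by side. With 20 participants, the reader could not tell whether a modest gap reflects the placement or the particular people studied. The answer is meant to guide where the device is worn.

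Both devices are worn on the same leg at the same time, so the data for a within-participant contrast will already exist.

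**Working it through.** **1. The plan's own figure.** The one calculated number behind the sample size is 12 subjects for r = 0.75, alpha 0.05 and power 0.9, taken from a cited study. By Fisher's z, n = ((z_alpha + z_power)/atanh(r))² + 3. One-sided, this is ((1.645 + 1.282)/0.973)² + 3 = 12.05, which reproduces the 12. Two-sided it gives 14.10; the documents do not state sidedness. The figure concerns a correlation, so it says nothing about the precision of a kappa or of a site difference. The recruited 20 rests on precedent.

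**2. What each objective receives.**
- Objective 1 (each site against observation): kappa, percentage agreement, Bland-Altman limits.
- Objective 2 (thigh against ankle, position and steps): no contrast, no interval for one, no rule for calling a site superior.
- Objective 3 (algorithm for sitting): percentage agreement of the algorithm against each single site.

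**3. How large a gap chance can produce.** The documents give no between-person variability, so the inputs here are assumptions:
- 20 participants and two sites of equal accuracy;
- mean probability of a correct reading 0.9 lying, 0.4 sitting, 0.9 standing, varying between people with intraclass correlation (ICC) 0.01, 0.05, 0.1 or 0.3;
- correlation between a person's two sites of 0 or 0.8;
- misreadings split evenly between the other two positions.

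With one-second rows, each person contributes 1,800 to 10,800 seconds. With event rows, each contributes seven events (3 lying, 2 sitting, 2 standing), with site errors independent given the person's accuracy.

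| Kappa gap between equally accurate sites | One-second rows | Event rows |
|---|---|---|
| 0.10 or more | about 0-16% of studies | about 10-22% |
| 0.22 or more | under 1% | under 1% |

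The 0.22 is the documents' only between-site kappa gap: ankle 0.43 minus waist 0.21 in the feasibility study. The top of the one-second range needs ICC 0.3 and uncorrelated sites; with low ICC or correlated sites the figure is near zero. In the event-row model, errors shared by the two sites would shrink the gaps.

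**4. Why the row and the unit of inference must be stated.** Take kappa 0.43 and assume chance agreement of 1/3. Observed agreement is 0.43 × 2/3 + 1/3 = 0.62. The 95% half-width with n independent rows is 1.96 × √(0.62 × 0.38/n)/(2/3).
- 140 rows (20 × 7 movements): ±0.12.
- 216,000 rows (20 × 10,800 seconds): ±0.003. This is a ceiling, since unobserved time is excluded.

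Seconds within a person are not independent. With design effect 1 + (10,800 − 1) × ICC:
- ICC 0.01: 108.99, effective n = 216,000/108.99 = 1,982, half-width ±0.03;
- ICC 0.30: 3,240.7, effective n = 66.7, half-width ±0.18.

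**5. Step counts.** A paired difference of signed errors does not measure accuracy, because the manual count cancels: (thigh − manual) − (ankle − manual) = thigh − ankle. The contrast has to use absolute error.

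**6. What a paired contrast can deliver.** For n = 20 the 95% half-width is t(19) × SD/√20 = 2.093/4.472 × SD = 0.468 × SD of the paired difference. An assumed SD of 0.15 gives 0.07; 0.30 gives 0.14.

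**The case against.** None of the four hypotheses claims that one of these two sites beats the other; they concern the ankle against observation, the algorithm and tolerability. Objective 2 can be read as descriptive, in an unfunded 20-patient PhD study. The feasibility work judged ankle against waist by setting kappa, bias and limits side by side, and the present plan yields the same quantities for thigh and ankle. For a gap as large as 0.22, that reading is adequate. This part of the objection stands, and it limits the point to modest gaps.

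Three stronger readings are tempting and should be resisted.

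- A reader might take the feasibility change in kappa from 0.43 to 0.48 as the gap that matters. That change came from recoding one reading of the ankle device. It is not a site comparison and gives no yardstick for one.
- A reader might infer that false claims of superiority are built in, because pooled seconds with a default standard error look far too precise. The plan states no between-site test and no such standard error. The overprecision is a reason to specify the method, not a defect of a stated analysis.
- A reader might say the kappa row could equally be seconds or events. The one-second capture, timing to the second, synchronised clocks and references to raw data all point to seconds. The row needs stating, but the likely intent is visible.

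**Conclusion.** The point holds as a gap between objective and analysis, and it should be fixed before the data are analysed. Objective 2 has no thigh-versus-ankle contrast for position or steps, and no interval is planned for kappa or percentage agreement. This follows from the text and does not depend on the simulation.

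The consequence is moderate. A gap near 0.22 would be convincing without a formal contrast. A gap around 0.10 would not always be: it arises between equally accurate sites in about 0-16% of simulated studies with one-second rows, the likelier choice, and 10-22% with event rows. These ranges rest on assumed ICCs, site correlations and reading accuracies, none of which the documents supply. The documents do not support saying that the plan will produce a wrong choice of site.

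**What to change.** In Statistical analysis:

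1. **Row and unit.** State the kappa row; one-second epochs of observed time appears to be the intent. Make the participant the unit of inference whichever row is used, and do not report the default epoch-level standard error or p-value.
2. **Per-site results.** Report each site's kappa and per-position agreement, with observed time in that position as denominator. Give 95% CIs from a bootstrap that resamples whole participants.
3. **Objective 2, position.** Add the paired thigh-minus-ankle difference, with 95% CI, in pooled kappa and in per-position agreement. Recompute both sites in each resample, so that a participant who missed a position still contributes the rest.
4. **Objective 2, steps.** Add the paired difference, with 95% CI, in absolute step-count error as a percentage of the manual count, beside the planned Bland-Altman results. The percentage is needed because distance walked varies and raw error grows with it.
5. **Check.** Give a t-interval on participant-level agreement differences among those who adopted the position. In simulation at n = 20 the percentile bootstrap was slightly liberal (per-site coverage 91.0-92.9%, against 94.5-95.8% for a t-interval on participant kappas). Say that the participant-level quantity differs slightly from pooled kappa: in the one-second model, mean participant kappa was about 0.52-0.53 and pooled kappa 0.54-0.55.

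The cost is SAP wording and a little more analysis, with no new data or patients. The interval may be inconclusive at n = 20, as the half-widths of 0.07 to 0.14 show; reporting that is more informative than two bare estimates.

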A feasibility study undertaken by the chief investigator (CI), as part of a PhD programme of study, determined that an ankle placement of the Actigraph GT3X accelerometer was superior to the waist for determination of body position and step count. In this study, thirty healthy adult volunteers simulated patients weakened by critical illness. They performed a movement protocol which incorporated the typical activities undertaken by patients recovering in hospital from critical illness. These included moving from lying to sitting, sitting to standing (and vice versa) and walking short distances. Video recordings were taken of each participant during the movement protocols, enabling observation of the body positions adopted and step counting during the walking activities. Video recording was used as the criterion measure for comparison against the data captured by the accelerometers worn both at the ankle and the waist. The activities detailed above are typically included within early mobility protocols which have undergone evaluation within populations experiencing critical illness (McWilliams et al., 2015, Adler and Malone, 2012, Schweickert et al., 2009). Moderate agreement ($\kappa = 0.43$, $p < 0.001$), was found between observation of video recordings of body position (lying, sitting or standing) and the inclinometer setting for the ankle placement. Fair agreement only ($\kappa = 0.21$, $p < 0.001$) was found for the waist placement. Regular misclassification of all body positions was found with the waist placement. The ankle placement identified both the lying and standing positions well. The sitting position however was only correctly identified intermittently for the ankle placement. A novel finding emerged from this research relating to the ankle placement site. When a side lying position was adopted, the ankle accelerometer inclinometer function regularly registered a '0'. The '0' setting normally corresponds to a 'not being worn' option. When a reading of '0' was recoded to the option 'side lying,' agreement improved from $\kappa = 0.43$ ($p < 0.001$) to $\kappa = 0.48$ ($p < 0.001$). This finding suggests a new way of interpreting the '0' reading of the inclinometer when worn on the ankle, which is worthy of further investigation within an actual patient population.

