3. To investigate the criterion validity of the combination of thigh and ankle accelerometer inclinometer outputs to correctly determine the sitting position. This

will determine whether an algorithm can be constructed using the two inclinometer readings, which will better distinguish the sitting from the standing position.

4. To evaluate, from a user perspective, the acceptability of these devices in relation to the placement sites used. This will be achieved by asking patients to score the answer to a particular question through the use of a Likert scale. The question is:
 - How would you rate the comfort of wearing the accelerometers?

In consideration of the results from the feasibility study undertaken by the CI and research using the addition of a thigh mounted accelerometer to identify the sitting position (Skotte et al., 2014), the following hypotheses can be constructed:

Hypotheses

1. An ankle mounted Actigraph GT3X accelerometer, will accurately identify both the lying and standing positions when compared with direct observation as a criterion measure.
2. An ankle mounted Actigraph GT3X accelerometer, will capture a step count comparable to that recorded by direct observation in a population resident on a hospital ward recovering from critical illness.
3. The combination of inclinometer outputs of both the thigh and ankle placement sites will permit development of an algorithm permitting the ability to better distinguish between the sitting and standing position.
4. The ankle and mid-thigh accelerometer placement sites will be well tolerated by patients recovering on a ward from critical illness.

Subject selection and involvement

The study will invite adult hospital ward patients recovering from critical illness to wear one Actigraph GT3X accelerometer on the antero-medial mid-thigh and another on the ankle, resting above the lateral malleolus of the same leg. The accelerometers will be worn for a period of time not exceeding three hours. Each device will be attached with a single patient use broad elastic belt, secured by Velcro fastening, using a standardised placement protocol. The non – dominant leg will be the preferred placement side.

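### The two-site sitting algorithm is built and scored in the same participants, so Objective 3 gives apparent agreement, and the comparison with single sites favours the algorithm

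*Combined protocol and SAP*

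**What the plan says.** Objective 3 (Defining the research question) is worded as validation: "To investigate the criterion validity of the combination of thigh and ankle accelerometer inclinometer outputs to correctly determine the sitting position". Its next sentence, and Hypothesis 3, are worded as development: "The combination of inclinometer outputs of both the thigh and ankle placement sites will permit development of an algorithm".

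The Categorical data part of the Statistical analysis section gives the sequence:

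- The rule comes from this study's own readings: "Examination of the inclinometer raw data captured from both placement sites will determine whether an algorithm can be constructed".
- Scoring depends on success in building it: "A further percentage agreement analysis will be undertaken if an algorithm can be constructed for determination of the sitting position".
- It is scored on this study's observations: "This algorithm will be compared against direct observational raw data identifying the sitting position only".
- It is set against the single sites: "This result will be compared against the percentage agreement of the individual placement sites in determination of the sitting position".
- The use made of that comparison is stated: "This will assist in determination of whether the algorithm is more superior to a single placement site".

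The Sample size calculation section gives one sample of 20, with no split. Under Study procedure, one investigator collects all the data and also does the analysis.

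**The concern.** The rule is chosen after looking at how the paired readings line up with observation in these participants, and is then credited with how well they line up in the same participants. The single-site readings get no such help, because their meaning is fixed by the device. Part of any gain shown by the algorithm can therefore come from fitting to features of these 20 people, such as leg posture or belt position, and would not carry over to the next patient.

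The protocol is more careful elsewhere. In the feasibility study, recoding the 0 reading as side lying after seeing the data raised kappa from 0.43 to 0.48, and the protocol treats that as something to be investigated further in actual patients. The two-site rule is given no such second step. What is at stake is whether Objective 3 can be reported as validity, and whether a claim that two devices beat one can rest on the planned comparison.

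**Working it through.** **Is building separated from testing anywhere?** No rule is written down in advance. The investigators' earlier data could not have supplied one: the feasibility study (described under The Actigraph GT3X accelerometer) used video for "comparison against the data captured by the accelerometers worn both at the ankle and the waist", with no thigh device. The cited study of a thigh-mounted device motivates the idea, but no rule is carried over from it. No hold-out, cross-validation, optimism correction or later sample appears.

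**Direction.** Each device has four readings (Data collection process), so there are 4 × 4 = 16 ankle-thigh reading pairs. For a given pair, let S be the seconds observed sitting and N the seconds observed not sitting. Calling the pair sitting gains S seconds of agreement; not calling it gains N. A rule fitted to maximise agreement gains max(S, N) in every pair. A single-site rule, such as sitting when the ankle reads 3, is one particular way of labelling the same 16 pairs, so in-sample it cannot exceed the fitted rule. A rule chosen less formally has no such guarantee, but it is still chosen with the answers in view.

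**Size.** The plan gives no agreement figure for the algorithm, so there is none to reproduce. Its only computed figure, 12 subjects for a correlation of 0.75, does not concern the algorithm. The size was therefore explored by simulation. From the documents: 20 participants, one-second epochs, four readings per site. Assumed: 600 seconds in each position per participant, and these average probabilities of readings 0, 1, 2, 3:

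| Position | Ankle | Thigh, informative | Thigh, uninformative |
|---|---|---|---|
| Lying | .30 .02 .60 .08 | .10 .05 .75 .10 | .10 .30 .40 .20 |
| Sitting | .05 .50 .10 .35 | .05 .10 .60 .25 | .10 .30 .40 .20 |
| Standing | .02 .90 .02 .06 | .02 .85 .03 .10 | .10 .30 .40 .20 |

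The ankle column follows the feasibility result in kind: lying and standing usually identified, sitting only at times. Each participant's own probabilities vary around these averages by a Dirichlet distribution; a smaller concentration means participants differ more. A pair is called sitting when S > N. Agreement was scored in the same participants and again leaving out one participant at a time (150 replicates per row, n = 20):

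| Thigh | Concentration | In-sample % | Left-out % | Difference | Ankle reading 3 alone % |
|---|---|---|---|---|---|
| Uninformative | 20 | 73.7 | 73.7 | 0.0 | 73.7 |
| Uninformative | 3 | 73.6 | 72.8 | 0.8 | 73.5 |
| Uninformative | 1 | 74.1 | 70.9 | 3.2 | 73.2 |
| Uninformative | 0.5 | 74.9 | 69.3 | 5.6 | 73.1 |
| Informative | 20 | 84.3 | 84.1 | 0.2 | 73.8 |
| Informative | 3 | 84.6 | 83.1 | 1.5 | 73.7 |
| Informative | 1 | 86.0 | 83.5 | 2.5 | 73.7 |
| Informative | 0.5 | 85.6 | 81.1 | 4.4 (before rounding) | 73.1 |

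With n = 12, an uninformative thigh and concentration 1, the difference was 6.3 points.

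In the fourth row the conclusion reverses: the algorithm appears better than the ankle alone by 74.9 − 73.1 = 1.8 points, but is worse by 73.1 − 69.3 = 3.8 points when scored on left-out participants. With an informative thigh and the same variation it does not reverse: the gain shrinks from 85.6 − 73.1 = 12.5 to 81.1 − 73.1 = 8.0 points.

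If agreement is counted over observed sitting seconds only, the in-sample minus left-out differences are 0.0, 0.9, 4.2 and 7.8 points (uninformative) and 0.3, 1.9, 3.5 and 6.1 points (informative), from low to high variation.

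**The case against.** The best defence is that this is a development step and is described as one. Objective 3 goes on to ask whether an algorithm can be built at all, Hypothesis 3 speaks of development, and the scoring is conditional. A development-sample figure is a legitimate first result from a 20-person doctoral study. That stands. What it does not cover is calling the figure criterion validity, or using it to weigh the algorithm against a single site.

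Two stronger readings are tempting. A reader might infer that the plan presupposes a superiority claim and will produce a false one. The text says only that the comparison will help to decide the matter; no test or threshold is set, and a genuinely useful thigh reading would survive proper validation, as the informative rows show. A reader might also infer a large bias from the 2^16 = 65,536 ways of labelling 16 pairs. That is a ceiling: the plan describes examining readings, not an unrestricted search, and a rule taken from the geometry of a seated leg leaves little room for overfitting. A simulation with weak paired readings (apparent balanced accuracy 0.66 to 0.71) gave about 1 to 9 points at n = 20, but the documents do not support so weak a signal and balanced accuracy is not the planned measure. With more informative readings, the same kind of exercise gave 0.5 to 2.7 points.

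A further caution stands. If agreement is taken over observed sitting only, a rule that over-calls sitting is not penalised for misclassified lying or standing, and cross-validation would not cure that.

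**Conclusion.** The point holds for the design and its direction. Followed as written, the plan yields apparent agreement, and sets a fitted rule against unfitted readings in the same people. The size is unknown. Under the assumed inputs at n = 20 it runs from near zero to several percentage points, depending on how much participants differ and how freely the rule is chosen. Because it depends on differences between about 20 people, the large number of one-second epochs does not remove it. The documents do not support saying that the algorithm will fail or that the bias is large; they support saying only that the planned figure cannot tell a real gain from a fitted one.

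**What to change.** In the Categorical data part of the Statistical analysis section, adopt one of two routes:

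- **(a)** Fix the two-site rule in writing before this study's paired readings are examined.
- **(b)** Write down in advance a mechanical rule-building procedure, for example giving each ankle-thigh reading pair the majority observed position, with a stated default for pairs not seen. Repeat it leaving out one participant at a time, apply each rule to the participant left out, and use the pooled left-out agreement as the Objective 3 result and in the comparison with single sites.

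Route (b) works only if the procedure is mechanical. A rule chosen by eye after seeing everyone cannot be cross-validated, because rerunning it removes no optimism.

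Under either route, label any in-sample figure as apparent agreement needing validation in new patients, and base no superiority conclusion on it.

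Cost: no extra participants or measurements. The rule or procedure must be drafted before the data are examined, route (b) adds up to 20 repeats of a tabulation, and the reported algorithm figure may be slightly less favourable.
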